4.1.2 Pre-Registration Exclusion Criteria

- 4.1.2.1 History of any colorectal cancer
- 4.1.2.2 History of other malignancy \leq 5 years prior to the Registration/Randomization evaluation, with the exception of basal cell or squamous cell skin cancer.
- 4.1.2.3 Presence of an active acute or chronic infection or uncontrolled illness including, but not limited to unstable congestive heart failure, unstable angina pectoris, cardiac arrhythmia, or psychiatric illness/social situations that would limit compliance with study requirements.
- 4.1.2.4 Acquired immunosuppressive diseases such as active HIV infection or congenital diseases of immunity.
- 4.1.2.5 History of heritable cancer syndrome (FAP, HNPCC).
- 4.1.2.6 History of auto-immune disease such as, but not restricted to, inflammatory bowel disease, systemic lupus erythematosus, rheumatoid arthritis, ankylosing spondylitis, scleroderma, multiple sclerosis, Hashimoto's thyroiditis, or Grave's disease.
- 4.1.2.7 Current or planned use of immunomodulators including: infliximab, 6-MP (mercaptopurine), methotrexate, cyclosporine, or other immunomodulatory drugs.
- 4.1.2.8 History of allergic reactions attributed to compounds of similar chemical or biologic composition to the study agent.
- 4.1.2.9 Pregnant women, because the teratogenic or abortifacient effects of the study agents remain incompletely defined.
- 4.1.2.10 Breastfeeding women, because there is an unknown but potential risk for adverse events in nursing infants secondary to treatment of the mother with the study agents.
- 4.1.2.11. Diagnosis of nonalcoholic steatohepatitis (NASH) and a NAFLD (nonalcoholic fatty liver disease) activity score (NAS) \geq 5. NOTES and EXCEPTIONS: NAS is based on findings from a liver biopsy. Participants with NAS of \leq 2 are eligible for enrollment. Participants with NAS of 3-4 must be discussed with the Principal Investigator and DCP before enrollment to consider other risk factors (i.e., obesity, alcohol intake). Participants with a prior diagnosis of NASH and no available NAS must be discussed with the Principal Investigator and DCP before enrollment to considered risk factors (i.e., obesity, alcohol intake). See Appendix F.

4.2 Registration/Randomization

4.2.1 Registration/Randomization Inclusion Criteria

- 4.2.1.1 ECOG performance status \leq 1 (Karnofsky \geq 70%; see Appendix A).
- 4.2.1.2 Hemoglobin greater than 90% of the lower limit of institutional normal.
- 4.2.1.3 Normal marrow and organ function, obtained \leq 28 days prior to Registration/Randomization, and defined as follows:
 - Platelets \geq 100 B/L (10^9 /L)
 - WBC $>$ 2.5 B/L (10^9 /L)
 - AST (SGOT), ALT (SGPT), alkaline phosphatase, total bilirubin, BUN, and creatinine \leq 1.5 x institutional upper limit of normal
- 4.2.1.4 ANA test result excludes overt autoimmune disease. Note: Test result may be reported in any of the following formats: \leq 1:160, negative, or $<$ 1.0.

4.2.2 Registration/Randomization Exclusion Criteria

- 4.2.2.1 Receiving any other investigational agent \leq 3 months prior to Registration/Randomization, except innocuous agents with no known interaction with the study agent (e.g., standard dose multivitamins or topical agents for limited skin conditions).
- 4.2.2.2 Any use of oral corticosteroids \leq 12 weeks prior to Registration/Randomization.

4.3 Inclusion of Women and Minorities

Both men and women and members of all races and ethnic groups are eligible for this trial. Refer to the Recruitment, Retention, and Adherence (RR&A) Plan Template for details (Appendix B).

4.4 Recruitment and Retention Plan

Each Participating Organization will be required to develop and submit a study- and site-specific RR&A plan for the purposes of insuring equal access to the clinical trial by individuals of all genders, races, and ethnic groups and for attaining the organization's accrual target. Participating Organizations will use the RR&A Plan Template (Appendix B) as the basis for their plans. At a minimum, these plans will be reviewed annually.

5. AGENT ADMINISTRATION

Intervention will be administered on an outpatient basis. Reported adverse events (AEs) and potential risks are described in Section 6.2. It should be noted that pharmacy personnel (or other appropriate personnel to whom this task is delegated) will not be blinded to the intervention assignment. Every effort should be taken to maintain the blinded nature of the study. For example, the time required to formulate and dispense the active injection should be no longer than the time to formulate and dispense the placebo injection.

5.1 Dose Regimen and Dose Groups

The vaccine will consist of 100 micrograms (0.1mg) of MUC1 100mer peptide dissolved in 50 microliters (0.05mL) of sterile saline, admixed with 500 micrograms (0.5mg) of the adjuvant poly-ICLC (Hiltonol®) in 250 microliters (0.25mL) volume, for a total injection volume of 300 microliters (0.3mL). Vaccine will be administered at weeks 0, 2, and 10 weeks. A booster vaccine will be administered at week 53 to establish the presence of T helper cell memory to the antigen. An identical-appearing placebo injection will be prepared using 0.9% NaCl.

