3. SUMMARY OF STUDY PLAN

3.1 Study Parts

There are 3 Parts planned. Each Part will provide salient data on MUC1 immunoprevention, with continuation through Part III providing insight on the clinical efficacy of the vaccine.

1. Part 1 will include participant follow up to week 12 and will permit assessment of MUC1 vaccine response compared to placebo.
2. Part 2 will include participant follow up to week 56 and will permit assessment of MUC1 immune memory response to a booster dose of vaccine compared to placebo.
3. Part 3 will include participant follow up to week 156 and will permit assessment of the clinical endpoint of adenoma recurrence in participants with vaccine compared to placebo. Assessment of MUC1 expression on recurrent adenomas will allow assessment of whether vaccination can impair MUC1 expression and adenoma progression.

The vaccine is manufactured at the FDA certified peptide facility of the University of Pittsburgh. The vaccine will consist of 100 micrograms (0.1mg) of MUC1 100mer peptide dissolved in 50 microliters (0.05mL) of sterile saline, admixed with 500 micrograms (0.5mg) of the adjuvant poly-ICLC (Hiltonol®) in 250 microliters (0.25mL) volume, for a total injection volume of 300 microliters (0.3mL). Poly-ICLC is a

TLR3 agonist, a synthetic, non-replicating dsRNA with no specific genetic message, which acts as a viral-mimic and activator of diverse elements of both the innate immune response and of adaptive immunity. Participants randomized to placebo will receive an identically appearing injection of sterile saline.

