6. PHARMACEUTICAL INFORMATION

6.1 Study Agent (IND # 15885, NCI, Division of Cancer Prevention)

MUC1 Peptide

The MUC1 peptide is composed of a 100 amino acids (aa). Representing five 20aa-long tandem repeats of the MUC1 VNTR region: H₂N-(GVTSAPDTRPAPGSTAPPAH)₅-CONH₂. The peptide is synthesized on a rapid multiple peptide synthesizer (Dupont NEN) in a dedicated facility under a strict and fully certified

procedure and using reagents with a defined expiration date. The peptide is highly hydrophilic and for testing as well as injection, it is dissolved in sterile saline. The peptide is tested for pyrogenicity and safety in guinea pigs, mice, and rabbits in accordance with an FDA approved protocol in a commercial facility. Once tested negative, it is aliquoted in small freezer vials containing one injection volume (100 mcg lyophilized peptide in 0.05 mL of sterile saline). Two percent of vials are sampled randomly for sterility testing in the University of Pittsburgh Medical center Microbiology Laboratories. Both 7 and 14-day sterility results are recorded. Peptide synthesis procedure, safety, pyrogenicity and sterility are contained in detail in [name] IND application to the FDA cross referenced by NCI, DCP. This peptide and all these procedures have been previously examined and approved by the FDA six times in six different IND applications. For administration as a vaccine, the peptide will be admixed with the POLY-ICLC adjuvant described above and below and injected subcutaneously as described above.

Poly ICLC

Poly-ICLC is supplied by Oncovir in vials containing 1 mL of 2 mg/mL opalescent white suspension. Poly-ICLC is withdrawn from the vial under sterile conditions and is to be administered intramuscularly, subcutaneously or intranasally as supplied. It can also be diluted with normal saline.

Each vial Poly-ICLC will be labeled with the following information:

- Drug Name
- Concentration
- Lot Number
- Date of Manufacture
- Manufacturer
- Investigational Use Statement

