6.6 Packaging and Labeling

Participating site pharmacy personnel will not be blinded to the study intervention. However, the pharmacy personnel will be required to label the injection supplied for each participant in such a manner as to not provide any information about intervention assignment to the site investigators. Each injection should be labeled according to institutional guidelines. The label should define the injection as MUC 1 100mcg/0.05mL w. poly-ICLC 500mcg/0.25mL or placebo 0.3mL. The label should also include the date of preparation, the route of administration, and the study name. The label may also include other information, such as the time of expiration, if required by local or state regulations.

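### The saline placebo is declared identical in appearance to a dose that is 83% opalescent white suspension, and no step in the plan masks the syringe

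*Combined protocol and SAP*

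**What the plan says.** The trial is described as double-blind (3.2). Two sections assert that the placebo matches the vaccine visually. Section 3.1: "Participants randomized to placebo will receive an identically appearing injection of sterile saline". Section 5.1: "An identical-appearing placebo injection will be prepared using 0.9% NaCl". Section 6.1 lists nothing in the placebo other than normal saline, which each participating organization provides.

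The pharmaceutical section describes the adjuvant differently: "Poly-ICLC is supplied by Oncovir in vials containing 1 mL of 2 mg/mL opalescent white suspension". In the active dose of 5.1, the peptide contributes only 0.05 mL and the adjuvant is the larger component: "admixed with 500 micrograms (0.5mg) of the adjuvant poly-ICLC (Hiltonol®) in 250 microliters (0.25mL) volume".

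The blinding safeguards are these:
- Section 5 has a general duty to protect the blind, with one example: "the time required to formulate and dispense the active injection should be no longer than the time to formulate and dispense the placebo injection".
- Section 6.6 says labels must not disclose the assignment, and then: "The label should define the injection as MUC 1 100mcg/0.05mL w. poly-ICLC 500mcg/0.25mL or placebo 0.3mL".
- Section 6.8.2.6 bars the contact who receives the assignment from assessing adverse events or other outcomes.

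Pharmacy staff are unblinded (5, 6.6). Section 5.2 leaves the injection to suitable site staff. It does not say whether they are blinded or kept apart from adverse-event assessment.

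**The concern.** If poly-ICLC looks as 6.1 says, plain saline cannot look identical to it unless something hides the contents. None of the listed safeguards concerns what is visible in the barrel. Section 6.8.2.6 shows that the authors recognised the principle, since it keeps the person who knows the assignment away from outcome assessment. The principle is not extended to the person who handles the syringe.

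The outcomes at stake are those that depend on judgement or self-report:
- Adverse events are graded, and attributed to study agent on a five-level scale (11.1.3, 11.1.4). Attribution decides whether an event counts toward the accrual-suspension rule, which is applied to each arm separately (13.7.1).
- Participants complete the Vaccine Report Card themselves (11.1.3.2), and its results are compared between arms (13.5, 13.7). Study staff also measure persisting reactions at Weeks 2 and 12 (7.3).
- Retention, and the timing of clinically scheduled colonoscopy in Part III, could shift if participants come to believe they know their arm. This is possible rather than shown.

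**Working it through.** **Inputs**
- Poly-ICLC as supplied: 2 mg/mL, opalescent white suspension (6.1).
- Poly-ICLC per dose: 0.5 mg in 0.25 mL (5.1).
- Peptide per dose: 0.05 mL in saline (5.1).
- Stated total active volume: 0.3 mL (5.1). Placebo volume: 0.3 mL (3.2).
- Injections: Weeks 0, 2, 10 and 53 (7.3), so up to four per participant.

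**Reproducing the plan's volumes**
- Poly-ICLC volume = 0.5 mg ÷ 2 mg/mL = 0.25 mL. This matches 5.1, so the suspension goes in at supplied strength.
- Total = 0.25 + 0.05 = 0.30 mL. This matches 5.1 and equals the placebo volume, so volume does not reveal the arm.

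**Composition of the active syringe**
- Suspension share = 0.25 ÷ 0.30 = 83.3%; placebo share = 0%.
- Dilution by the peptide saline = 0.30 ÷ 0.25 = 1.2-fold.
- Poly-ICLC concentration in the mixture = 0.5 ÷ 0.30 = 1.67 mg/mL, against 2 mg/mL as supplied.

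**Appearance statements side by side**

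| Section | Statement about appearance or form |
|---|---|
| 2.2 | Poly-ICLC vial holds a solution |
| 3.1, 5.1 | Saline placebo looks identical to the vaccine |
| 6.1 | Poly-ICLC is an opalescent white suspension |
| Any section | No description of the final mixture |

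Section 6.1 gives the only explicit visual description of the adjuvant. A 1.2-fold dilution is unlikely to remove that appearance, but this is an inference.

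**Does any safeguard cover the contents?**

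| Safeguard | What it covers | Syringe contents hidden? |
|---|---|---|
| Preparation time (5) | Waiting time | No |
| Label (6.6) | Text on the syringe | No |
| Assignment contact (6.8.2.6) | One person's role | No |
| General duty (5) | Intent, no method | Not specified |

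**Sensitivity of the suspension rule**
Among the first 10 treated participants in an arm, 2 with a grade 3 or higher event that is at least possibly related suspend accrual (13.7.1). Moving one such participant's event between unlikely and possible changes the count by 1, which is half of the trigger.

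**The case against.** **What stands.** The documents never show the mixed product, never say that saline is clear, and in 2.2 call poly-ICLC a solution. The 83% is a volume share, not a measure of visibility. A participant sees one syringe with no comparator. Section 5.1 can also be read as telling the unblinded pharmacy to make the injections look alike by its own means, and a site could mask locally. These points limit the conclusion to a possible failure of the blind. They do not supply the missing step.

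Injection-site reactions are a separate and perhaps larger route to unblinding. Most pilot participants had erythema with soreness (2.3), and 6.2 puts redness, pain and flu-like symptoms above 20 in 100. Masking cannot address that. Reactions, however, follow dosing and vary between people, whereas the syringe is visible beforehand and differs systematically by arm.

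**Stronger readings that the documents do not support.**
- *The preparation-time rule runs the wrong way.* A reader might infer this because the active dose is stored frozen and must be mixed. But requiring active time to be no longer than placebo time is the same inequality as requiring placebo time to be at least active time. Section 6.3 also allows preparation within 8 hours before administration, so the time need not be visible to anyone.
- *The label rule discloses the arm.* The label sentence could be taken as two arm-specific texts. Read after the instruction that labels must not disclose assignment, it is more naturally one either/or text. Only a clarification is warranted.
- *Every syringe is distinguishable.* About 110 participants × 4 injections gives 440 at most, before the assumed dropout of up to 10% by year 1. That counts opportunities to see a syringe and does not measure bias.
- *The efficacy results are compromised.* The primary endpoint and the Part I and II key secondary endpoints are ELISA titers. Recurrence is abstracted from operative and pathology reports (7.6.2), and nothing has endoscopists or pathologists handling study syringes.

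**Conclusion.** The point holds in limited form. The claim of identical appearance in 3.1 and 5.1 conflicts with the description in 6.1 of a component that fills 83% of the active syringe at a 1.2-fold dilution. No stated procedure resolves the conflict. The injector, and possibly the participant, may be able to infer the arm at up to four injections, starting with the first.

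This rests on two assumptions that the documents do not state: that 0.9% NaCl is clear, and that the mixture keeps the adjuvant's opalescence. Both can be checked by preparing one syringe of each. If 2.2 were right and the mixture proved clear, the concern would fall away and only the wording would need correcting.

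The exposure lies in adverse-event grading and attribution, the suspension rule that depends on them, and the Vaccine Report Card, with a possible effect on retention and colonoscopy scheduling. The size of any bias cannot be calculated from the documents. The ELISA endpoints are little affected, and the sample size and power statements are unaffected.

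**What to change.** 1. In 3.1 and 5.1, replace the identical-appearance wording with *equal-volume, visually masked*.
2. In 6.6, require the unblinded pharmacy to dispense both arms in opaque-sleeved or opaque-taped syringes.
3. Reconcile 2.2 with 6.1 on the form of poly-ICLC, and state how the final mixture looks.
4. As a clarification only, state in 6.6 that one verbatim either/or label text goes on every syringe in both arms.
5. Acknowledge as a limitation that injection-site reactions may still reveal the arm.

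The preparation-time rule in Section 5 needs no change. Doses, volumes, sample size and analyses also stay as they are. The cost is the sleeves or tape, a little pharmacy time, and the wording edits.

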5.2 Vaccine Administration

The vaccine will be administered by appropriate site personnel subcutaneously in the anterior thigh approximately 20 cm inferior to the inguinal ligament. The vaccine will be administered into the same thigh on all 4 occasions for vaccine delivery. The vaccine site may demonstrate erythema after administration. This erythema can persist even to the timing of the next vaccine dosing. Erythema is not a contraindication to repeat vaccination. However, at the discretion of the investigator, repeat vaccination may be delayed, but not to exceed the protocol limits. It is also possible to inject the vaccine

into the opposite thigh, if necessary. Preferred windows for visits and vaccine administration and sampling are provided in Section 7.1.

5.3 Run-in Procedures

Not applicable.

5.4 Concomitant Medications

All medications (prescription and over-the-counter), vitamin and mineral supplements, and/or herbs taken by the participant will be documented on the concomitant medication CRF and will include: start and stop date, dose and route of administration, and indication.

If a study participant is prescribed corticosteroids or immunomodulators during the course of the study, the situation will be discussed among the treating physician, the study chair, and the medical monitor to determine whether or not the participant should be allowed to continue on study.

5.5 Contraindications

Contraindications to study participation include receiving other investigational agents, presence or occurrence of an active acute or chronic infection or undercurrent illness, use of immunomodulators pregnancy, or breastfeeding (as applicable). See Section 4.2 for details regarding initial eligibility.

5.6 Dose Modification

The vaccine will be administered in the protocol-defined dosage for all participants on all occasions.

5.7 Adherence/Compliance

5.7.1 All vaccine/placebo will be administered by appropriately trained study personnel at each site. Vaccine/placebo administration will be documented on the Intervention Administration CRF.

5.7.2 Individuals who receive the Week 0, Week 2, and Week 10 injections will be considered evaluable for the primary endpoint. Individuals who receive the Week 53 injection will be considered evaluable for the Part II key secondary endpoint. Individuals from whom data and specimens are collected for a subsequent clinical colonoscopy occurring at least 1 year (52 weeks) after the Week 0 injection will be considered evaluable for the Part III key secondary endpoint.

6. PHARMACEUTICAL INFORMATION

6.1 Study Agent (IND # 15885, NCI, Division of Cancer Prevention)

MUC1 Peptide

The MUC1 peptide is composed of a 100 amino acids (aa). Representing five 20aa-long tandem repeats of the MUC1 VNTR region: H₂N-(GVTSAPDTRPAPGSTAPPAH)₅-CONH₂. The peptide is synthesized on a rapid multiple peptide synthesizer (Dupont NEN) in a dedicated facility under a strict and fully certified

procedure and using reagents with a defined expiration date. The peptide is highly hydrophilic and for testing as well as injection, it is dissolved in sterile saline. The peptide is tested for pyrogenicity and safety in guinea pigs, mice, and rabbits in accordance with an FDA approved protocol in a commercial facility. Once tested negative, it is aliquoted in small freezer vials containing one injection volume (100 mcg lyophilized peptide in 0.05 mL of sterile saline). Two percent of vials are sampled randomly for sterility testing in the University of Pittsburgh Medical center Microbiology Laboratories. Both 7 and 14-day sterility results are recorded. Peptide synthesis procedure, safety, pyrogenicity and sterility are contained in detail in [name] IND application to the FDA cross referenced by NCI, DCP. This peptide and all these procedures have been previously examined and approved by the FDA six times in six different IND applications. For administration as a vaccine, the peptide will be admixed with the POLY-ICLC adjuvant described above and below and injected subcutaneously as described above.

Poly ICLC

Poly-ICLC is supplied by Oncovir in vials containing 1 mL of 2 mg/mL opalescent white suspension. Poly-ICLC is withdrawn from the vial under sterile conditions and is to be administered intramuscularly, subcutaneously or intranasally as supplied. It can also be diluted with normal saline.

Each vial Poly-ICLC will be labeled with the following information:

- Drug Name
- Concentration
- Lot Number
- Date of Manufacture
- Manufacturer
- Investigational Use Statement

Low-dose Poly-ICLC administered IM or SC or intranasally has been well tolerated in clinical trials of patients with brain tumors, other cancers, multiple sclerosis, and in normal volunteers. Multiple additional trials have used it in combination with various cancer or HIV vaccines. The most common adverse events experienced in these studies have been transient discomfort at the injection site and transient malaise. Subcutaneous injection may result in a transient erythematous skin reaction. Preliminary findings from these trials suggest that low-dose Poly-ICLC may be effective in treating various tumors and further study is warranted.

Poly ICLC synthesis, procedure, safety, pyrogenicity, and sterility are contained in detail in the Oncovir IND and DMF to the FDA cross-referenced by NCI, DCP.

Placebo

The placebo injection will contain normal saline (0.9% NaCl) provided by each individual Participating Organization.

6.2 Reported Adverse Events and Potential Risks

The side effects listed in the table below are based on a variety of previous studies that were similar to this study in some ways but different in important ways (including stronger doses) that may have led to different side effects. In the previous study that was most similar to this study, no autoimmune disease or serious side effects were identified.

Possible Side Effects of the MUC1 – poly-ICLC vaccine:

Common, Some May Be Serious In 100 people who receive the injection, more than 20 may have:

• Redness at injection site (erythema)• Pain/soreness at injection site• Flu-like symptoms, which may include fever chills, headache, fatigue, muscle pain, and joint pain• Night sweats• Loss of appetite• Low albumin blood test result (a type of protein in the blood)

The redness and soreness generally resolve within a few days to a week. Generally, acetaminophen (Tylenol®) is sufficient for pain relief. The flu-like symptoms generally resolve within 12-24 hours. Acetaminophen (Tylenol®) generally helps with these symptoms if they occur.

Occasional, Some May Be Serious In 100 people who receive the injection, 4 to 20 may have:

• Low white blood cell count (cells that fight infections)• Low platelet count (cells that help the blood clot in order to stop bleeding)• Anemia (which may cause tiredness, or may require blood transfusion)• Abnormal liver function test results

Rare, Some May Be Serious In 100 people who receive the injection, 3 or fewer may have:

• Hives, shortness of breath, or an allergic reaction that is life-threatening• Immune reaction to his or her own tissue (autoimmune diseases) or if present, may be made worse.

